2 STUDY OBJECTIVES

2.1 Primary

• To compare the efficacy of troriluzole (140 mg once daily) versus placebo on ataxia symptoms in subjects with spinocerebellar ataxia (SCA) after 8 weeks of treatment as measured by the total score on the Scale for the Assessment and Rating of Ataxia [SARA]

2.2 Secondary

- To assess the safety and tolerability of troriluzole in subjects with SCA
- To compare efficacy of troriluzole with placebo on patient impression of benefit via use of the PGI-C

[figure not shown]
3 STUDY ENDPOINTS

3.1 Primary

• The total score on the Scale for the Assessment and Rating of Ataxia (SARA).

3.2 Secondary

- Tolerability and safety of troriluzole will be measured by the frequency and severity of adverse events and discontinuations of adverse events.
- Patient Global Impression of Change (PGI-C);

3.4 Measures of Interest

- Safety and Other assessments:
 - Sheehan Suicidality Tracking Scale (STS)
 - o ECG assessments;
 - o Vital Sign and Physical Measurements;

4 STUDY PLAN

4.1 Study Design and Duration

BHV4157-201 is a Phase IIb/III, multicenter, randomized, double-blind, 2-arm placebo-controlled parallel-group study designed to assess safety, tolerability, and efficacy in a population of patients with Spinocerebellar Ataxia. Subjects will be randomized to receive placebo (QD) or troriluzole (140 mg QD),

Subjects with SCA3 genotype will be limited to comprise up to approximately 10% so that this most common type of SCA is not over-represented.

Dosing will continue for 8 weeks. Subjects will return to the clinic two weeks after discontinuing study medication for a follow-up safety visit. In addition, subjects completing the Randomization Phase will be offered approximately 192 weeks of open-label treatment as long as the PI believes open-label treatment offers an acceptable risk-benefit profile. Subjects who agree to enter the Extension Phase will not complete the follow-up safety visit and should continue dosing as specified.

Subjects entering the Extension Phase would have their first Extension Visit four weeks after the Week 8 Randomization Phase visit. If there is a delay of two weeks or more in dosing between the Randomization Phase and the Extension Phase, subjects would be required to complete an Extension Baseline Visit. Thereafter, subjects will undergo visits every fourth week through Week 12 of this phase. Then subjects will undergo visits every 12 weeks up to Week 192 of this phase. All subjects will undergo a termination visit two weeks after the last dose of study drug.

Subjects who previously completed the extension phase will be allowed to participate in the expanded extension phase for a total of 144 weeks of open-label administration of troriluzole, provided the PI deems this treatment to present an acceptable risk-benefit profile. Such subjects who have been off of medication for at least 2 weeks, will need additional Baseline Visits followed by visits scheduled approximately every 12 weeks, as well as laboratory assessments at approximately 4 and 8 weeks after re-starting medication. In addition, these subjects will be required to have clinical laboratory assessment results that are not deemed clinically significant, available prior to the Baseline Visit and drawn within 6 weeks prior to that visit. These subjects should not have taken riluzole for at least 12 hours prior to re-starting troriluzole.

[figure not shown]
For subjects who experienced decline (as defined below) over at least 9 months of treatment with 140 mg troriluzole, the PI may offer an increased dose of 280 mg daily based on anticipated tolerability (e.g., the patient was tolerating the 140 mg dose well). Decline will be defined as demonstration of a 2 point or greater decline from baseline on the SARA scale on two most recent consecutive visits (at least one month apart) accompanied by PI opinion clinical worsening. Patients who do not tolerate 280 mg daily or demonstrate clinically significant lab abnormalities may have their dose adjusted to 140 mg daily. Subjects who increase to 280 mg daily will have lab tests at approximately 4, 8 and 12 weeks after the dose increase, then no less often that approximately every 12 weeks. Subjects who are given a trial

of 280 mg daily troriluzole will require additional clinical lab assessments (LFTs) at approximately 4 and 8 weeks after starting the increased dosing. For subjects who were tolerating 140 mg without adverse effects, the dose increase may occur at the usual dosing time. Some subjects may better tolerate dosing at bedtime to minimize any impact of sedation. In addition, the PI may split doses (twice daily) if adverse events suggest that this could enhance tolerability. Dosing regimen should be recorded in the CRF.

Subjects will be assessed at clinic visits per the Schedule of Assessments/Time & Events.

4.2 Study Schematic

Figure 4. Study Schematic

R, Signifies randomization

^{*,} Eligible subjects will include those who perceived benefit in earlier phases or for whom the PI believes extended treatment with troriluzole would offer an acceptable risk-benefit profile.

^{#,} Maximum duration of troriluzole treatment of 192 weeks (not required to be continuous dosing weeks if subjects already completed 48 Week Extension Phase).

^{^,} As per Protocol, subjects demonstrating decline on at least 9 months of 140 mg troriluzole may be offered a higher dose of 280mg daily.

4.3 Schedule of Assessments

Table 2. Schedule of Assessments and Events - Randomization Phase

	SCR	Baseline	Wk 4	Wk 8	2-Wk Post Last Dose (ONLY for subjects NOT entering extension phase or who discontinue early)	Additional Instruction
Visit	Visit 1	Visit 2	Visit 3	Visit 4	Visit 5	
Eligibility Assessments						
Informed Consent	Х					
Inclusion/Exclusion	Х					Should be re-reviewed at Baseline
Medical History	Х					
Demographic Assessment	Х					
Disease History	Х					
Neurological Exam	Х			Х		
Mini Mental State Exam (MMSE)	Х					
Pregnancy Test for WOCBP (serum)	X	Х		Х		
Pregnancy Test for WOCBP (urine)	^	X	Х	^		To be done within 72 hours prior to dosing at visit 2 (Baseline Visit). The site may test a patient at any time if they suspect the patient may be pregnant.
Safety Assessments						, , , , , , ,
Laboratory Assessments including						No fasting required
urinalysis	Х	Х		Х	X	ino iasting required
Serum Chemistry			х			A physician who is not the SARA rater must b available to review lab tests and manage any potential medical evaluation throughout the randomization phase
Physical Exam						PE will be done at W4 if warranted by
	Х			Х		emergence of new AE's
Physical Measurements	Х	Х	X	X		
Vital Signs	Х	Х	Х	Х		
12-Lead ECG	Х			Х		
		X	Х	Х	X	
Concomitant Medication Review	Х	^				
	X	X	X	X	X	
Concomitant Medication Review Adverse Event Assessments Sheehan Suicidality Tracking Scale (STS)	X		X	×	X	
Concomitant Medication Review Adverse Event Assessments Sheehan Suicidality Tracking Scale		х				This should be the first clinical outcome

Visit Window is +/- 2 days during the Randomization Phase

Table 3. Schedule of Assessments and Events - Extension Phase

	¹ Baseline Visit	Ext. Wk 4	Ext. Wk 8	Ext. Wk 12	Ext. Wk 24	Ext. Wk 36	Ext. Wk 48
Visit		Visit 1	Visit 2	Visit 3	Visit 4	Visit 5	Visit 6
Eligibility Assessments							
⁴ Informed Consent	Х						
Neurological Exam					Х		Х
Pregnancy Test for WOCBP (serum)	Х				Х		Х
² Pregnancy Test for WOCBP (urine)	Х	Х	Х	Х		Х	
Safety Assessments							
Laboratory Assessments including urinalysis	х				Х		Х
³ Lab: LFT tests only (ALT, AST, BILI, GGT)		х	Х	Х		Х	
Physical Exam	Х				Х		Х
Physical Measurements	V	V	V	V	V	V	V
Vital Signs	X	X	X	X	X	X	X
12-Lead ECG	X	^	^	^	X	^	X
Concomitant Medication Review	X	X	Х	X	X	X	X
Adverse Event Assessments	х	х	х	х	х	х	Х
Sheehan Suicidality Tracking Scale (Sheehan STS)	X	X	Х	Х	Х	Х	Х
* Clinical Outcome Assessment							
SARA	х		X		х	Х	Х
Clinical Drug Supply							

¹ Baseline visit for the Extension Phase is *only required* if there is an extended break (≥2 weeks) in dosing between the Randomization and Extension Phases.

Χ

Χ

Х

Х

X

Χ

Χ

Dispense Study Drug

Drug Accountability

² Subjects will be provided with pregnancy tests to take in between every 3-month office visit. Subjects should be instructed to contact if they become pregnant at any time during the study.

³, Subjects whose dose is increased to 280 mg daily will require LFT tests approximately 4 and 8 weeks after the increase and then approximately every 12 weeks thereafter

Table 4. Schedule of Assessments and Events - 144-Week Expanded Extension Phase (continuing subjects)

	Exp.Ext. Wk 60	Exp. Ext. Wk 72	Exp. Ext. Wk 84	Exp. Ext. Wk 96 or early discontinuation visit (less than or equal to EE Wk 96)
Visit	Visit 7	Visit 8	Visit 9	Visit 10
Eligibility Assessments				
Neurological Exam		Х		X
Pregnancy Test for WOCBP (serum)		X		X
¹ Pregnancy Test for WOCBP (urine)	×		X	
Safety Assessments				
Laboratory Assessments including urinalysis		X		X
² Lab: LFT tests only (ALT, AST, BILI, GGT)	X		Х	
Physical Exam		X		X
Physical Measurements	Х	Х	Х	Х
Vital Signs	Х	Х	Х	Х
12-Lead ECG		X		X
Concomitant Medication Review	Х	Х	X	х
Adverse Event Assessments	X	X	X	×
Sheehan Suicidality Tracking Scale (Sheehan STS)	х	х	Х	х
* Clinical Outcome Assessment				
SARA	Х	X	Х	X
Clinical Drug Supply				
Dispense Study Drug	Х	Х	Х	
Drug Accountability	X	Х	Х	Х

⁴ Informed Consent for continuing subjects entering the expanded extension phase will be obtained at next scheduled visit. Visit window is +/- 7 days during the extension phase.

	EE Wk108	EE Wk 120	EE Wk 132	EE Wk 144
Visit	Visit 11	Visit 12	Visit 13	Visit 14
Eligibility Assessments				
Neurological Exam		Х		Х
³ Pregnancy Test for WOCBP (serum)	Х	х	Х	X
Safety Assessments				
^{2, 3} Lab: LFT tests only (ALT, AST, BILI)	Х	х	Х	×
Physical Exam		Х		Х
Physical Measurements	Х	Х	Х	Х
Vital Signs	Х	Х	Χ	X
12-Lead ECG		X		X
Concomitant Medication Review	X	X	X	X
Adverse Event Assessments	Х	х	Х	х
Sheehan Suicidality Tracking Scale (Sheehan STS)	Х	х	Х	Х
Clinical Outcome Assessments				
SARA	Х	Х	Χ	X
Clinical Drug Supply				
Dispense Study Drug ⁴	Х	Х	X	
Drug Accountability	X	X	Χ	X

	EE Wk 156	EE Wk 168	EE Wk 180	EE Wk 192 or Early Discontinuation	EE 2-Wk Post Last Dose
Visit	Visit 15	Visit 16	Visit 17	Visit 18	Visit 19
Eligibility Assessments					
Neurological Exam		Х		Х	
³ Pregnancy Test for WOCBP (serum)	×	Х	Х	x	
Safety Assessments					
^{2, 3} Lab: LFT tests only (ALT, AST, BILI)	×	Х	Х	x	X
Physical Exam		Х		Х	
Physical Measurements	Х	Х	Х	X	
Vital Signs	Х	Х	Х	X	
12-Lead ECG		Х		X	
Concomitant Medication Review	×	×	×	x	x
Adverse Event Assessments	Х	Х	Х	Х	Х
Sheehan Suicidality Tracking Scale (Sheehan STS)	х	х	х	х	Х
Clinical Outcome Assessments					
SARA	Х	Х	Х	X	Х
Clinical Drug Supply					
Dispense Study Drug ⁴	Х	Х	Х		
Drug Accountability	Х	Х	Х	X	

¹ Subjects will be provided with pregnancy tests to take in between every 3-month office visit. Subjects should be instructed to contact if they become pregnant at any time during the study. Pregnancy testing in between visits is not required EE Week 108 through EE 2-Week Post Dose.

Visit window is +/- 7 days during the extension phase.

² Subjects whose dose is increased to 280 mg daily will require LFT tests approximately 4 and 8 weeks after the increase and then approximately every 12 weeks thereafter

³ Lab will not be done by a Central Lab and must be done at local lab.

⁴ If the study site needs to send drug overnight via certified and tracked courier and this is acceptable to the institution because a visit is absolutely not possible because of the COVID-19 pandemic, this is permissible per study. The sponsor should be consulted prior to shipping drug.

Table 5. Schedule of Assessments and Events – 144 -Week Expanded Extension Phase (returning subjects)

	1							
	¹ Baseline Visit 1	² Baseline Visit 2	Exp.Ext. Wk 4	Exp. Ext. Wk 8	Exp. Ext. Wk 12	Exp. Ext. Wk 24	Exp. Ext. Wk 36	Exp. Ext. Wk 48 or early discontinuation (less than or equal to EE Wk 48)
Visit	Visit EE1	Visit EE2	Visit EE3	Visit EE4	Visit EE5	Visit EE6	Visit EE7	Visit EE8
Eligibility Assessments								
Informed Consent	Х							
⁵ Neurological Exam	X					X		X
Pregnancy Test for WOCBP (serum)						X		X
³ Pregnancy Test for WOCBP (urine)	Х				Х		Х	
Safety Assessments								
⁶ Laboratory Assessments including	х	х				X		X
⁴ Lab: LFT tests only (ALT, AST, BILI, GGT)			Х	X	Х		Х	
Physical Exam	X					X		X
Physical Measurements	Х				Х	Х	Х	Х
Vital Signs	Х				Х	Х	Х	Х
12-Lead ECG						X		X
Concomitant Medication Review	х				Х	Х	×	×
Adverse Event Assessments					х	x	x	×
Sheehan Suicidality Tracking Scale (Sheehan STS)	X				Х	х	Х	X
* Clinical Outcome Assessment								
SARA		Х			Х	X	Х	X
Clinical Drug Supply								
Dispense Study Drug		Х			Х	Х	Х	
Drug Accountability					X	Х	Х	Х
	L	1	l		1	l		l

			1		•
	Exp. Ext. Wk 60	Exp. Ext. Wk 72	Exp. Ext. Wk 84	Exp. Ext. Wk 96	Exp. Ext. 2-Wk Post Last Dose
Visit	Visit EE 9	Visit EE 10	Visit EE 11	Visit EE 12	Visit EE 13
Eligibility Assessments					
Neurological Exam		Х		Х	
⁷ Pregnancy Test for WOCBP (serum)	Х	Х	Х	Х	
Safety Assessments					
^{4,7} Lab: LFT tests only (ALT, AST, BILI)	Х	Х	Х	Х	Х
Physical Exam		Х		Х	
Physical Measurements	Х	Х	Х	X	
Vital Signs	Х	Х	Х	X	
12-Lead ECG		Χ		X	
Concomitant Medication Review	×	X	×	X	X
Adverse Event Assessments	×	×	×	х	×
Sheehan Suicidality Tracking Scale (Sheehan STS)	х	Х	х	Х	X
Clinical Outcome Assessments					
SARA	Х	Х	Х	Х	Х
Clinical Drug Supply					
Dispense Study Drug ⁸	Х	Х	X		
Drug Accountability	X	X	X	X	

	Exp. Ext. Wk 108	Exp. Ext. Wk 120	Exp. Ext. Wk 132	Exp. Ext. Wk 144 or Early Discontinuation	Exp. Ext. 2-Wk Post Last Dose
Visit	Visit EE 9	Visit EE 10	Visit EE 11	Visit EE 12	Visit EE 13
Eligibility Assessments					
Neurological Exam		Х		X	
⁷ Pregnancy Test for WOCBP (serum)	Х	Х	Х	Х	
Safety Assessments					
^{4,7} Lab: LFT tests only (ALT, AST, BILI)	Х	Х	Х	Х	Х
Physical Exam		Х		X	
Physical Measurements	Х	Х	Х	X	
Vital Signs	Χ	Х	Х	X	
12-Lead ECG		Х		Х	
Concomitant Medication Review	X	X	×	X	x
Adverse Event Assessments	X	×	×	x	X
Sheehan Suicidality Tracking Scale (Sheehan STS)	Х	Х	х	х	Х
Clinical Outcome Assessments					
SARA	Х	Х	Х	Х	Х
Clinical Drug Supply					
Dispense Study Drug ⁸	Χ	X	Х		
Drug Accountability	X	X	Х	X	

¹ Baseline 1 and Baseline 2 visits for the 48-Week Expanded Extension Phase are *only required* for subjects re-entering the study.

²Baseline 2 visit for the Extension Phase is *only required* if results of Baseline 1 visit meet study eligibility criteria.

³ Subjects will be provided with pregnancy tests to take in between every 3-month office visit. Subjects should be instructed to contact if if they become pregnant at any time during the study. Pregnancy testing in between visits is not required EE Week 60 through EE 2-Week Post Dose.

⁴ Subjects whose dose is increased to 280 mg daily will require LFT tests approximately 4 and 8 weeks after the increase and then approximately every 12 weeks thereafter. Subjects re-entering the extension phase will require LFT tests approximately 4 and 8 weeks after dosing is re-started.

⁵ Neurological exam is required for subjects whose Baseline 2 visit is greater than 7 days after Baseline 1.

⁶ Safety Laboratory Assessments are required for subjects whose Baseline 2 visit is greater than 7 days after Baseline 1. Repeat of BL visit 1 labs can be done with permission from Sponsor.

⁷ Lab will not be done by a Central Lab and must be done by local lab.

⁸ If the study site needs to send drug overnight via certified and tracked courier and this is acceptable to the institution because a visit is absolutely not possible because of the COVID-19 pandemic, this is permissible per study. The sponsor should be consulted prior to shipping drug. Visit window is +/- 7 days during the extension phase.

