4.3.3 Extension Phase (if applicable)

The Extension Phase includes a Baseline Visit; however, that visit is only required if there is a break in dosing two weeks or greater between the Week 8 Visit in the Randomization Phase and the Week 4 visit in the Extension Phase. The Extension Phase also includes a Baseline Visit 1 and Baseline Visit 2; however those visits are only required for subjects who have previously completed the 2 week post-dose visit in the Extension Phase, and who will be reentering the extension phase of open-label treatment beginning at Week 60 through Week 144. Subjects re-entering the extension phase will complete the Baseline 1 visit to confirm that they meet safety eligibility requirements, then return for the Baseline 2 visit, followed by visits scheduled approximately every 12 weeks, as well as laboratory assessments at approximately 4 and 8 weeks after re-starting medication. Thereafter, subjects will undergo visits every 12 weeks up to Week 144 of the Extension Phase (or 192 weeks for continuing subjects). All subjects will undergo a termination visit two weeks after the last dose of study drug.

Please refer to the Schedule of Assessments/Time & Events for details on procedures during the Extension Phase. There is a visit window of +/- 7 days during the Extension Phase of the study.

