4.4 Post Study Access to Therapy (if applicable)

There is an extension phase of this trial for up to 192 weeks (144 weeks for returning subjects) as described in section 4.3.3. No other study drug access is available after the extension.

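### Tables 4 and 5 mark no drug dispensing at four mid-phase Expanded Extension visits, which conflicts with the planned open-label duration and could put undetected off-drug data into the long-term summaries

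*Protocol*

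**What the plan says.** **Treatment duration.** For continuing subjects Section 4.1 states: "Then subjects will undergo visits every 12 weeks up to Week 192 of this phase". It admits returning subjects "for a total of 144 weeks of open-label administration of troriluzole". Section 4.3.3 repeats the 12-weekly schedule: "Thereafter, subjects will undergo visits every 12 weeks up to Week 144 of the Extension Phase (or 192 weeks for continuing subjects". Section 4.4 gives the same two limits: "There is an extension phase of this trial for up to 192 weeks (144 weeks for returning subjects".

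**Dispensing.** Tables 4 and 5 lay out the Expanded Extension in six blocks, three per table. In every block the dispensing row is marked at the 12-weekly visits except the last on-treatment column, where it is blank while drug accountability is marked. Two of these six columns are the real end of dosing: Wk 192 in Table 4 and Wk 144 in Table 5. The other four are followed by further treatment visits. Of those four, one is headed "Exp. Ext. Wk 96 or early discontinuation visit (less than or equal to EE Wk 96" (Table 4) and one "Exp. Ext. Wk 48 or early discontinuation (less than or equal to EE Wk 48" (Table 5). Table 4 Wk 144 and Table 5 Wk 96 carry no early-discontinuation label.

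**Visit labels.** Table 5 places a two-week post-last-dose column after Wk 96, then continues to Wk 108. It numbers Wk 108 to Wk 144 and their post-dose visit EE 9 to EE 13, numbers already used for Wk 60 to Wk 96 and their post-dose visit.

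**Analysis rules.** Section 4 of the SAP addendum names two dosing breaks: between the Randomization and Extension Phases, and before the Expanded Extension. For efficacy, a visit is on-treatment if it falls no later than 7 days after the final dose.

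**The concern.** The schedule is what a site works from when it supplies drug. Followed literally, it has a continuing or returning subject hand back drug at a mid-phase visit, receive none, and be assessed 12 weeks later, when dispensing resumes. The narrative sections describe no such pause.

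If a pause occurred, the analysis rules would not detect it. The on-treatment definition looks only at the final dose, so a SARA score taken after weeks without drug is on-treatment whenever dosing later resumes. The overall compliance formula in SAP Section 4.8.1 removes only the Randomization-to-Extension break. If some sites dispensed at these visits and others did not, exposure would differ between sites without the long-term summaries showing it.

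**Working it through.** **Inputs.** Dispensing marks come from Tables 4 and 5, planned duration from Sections 4.1, 4.3.3 and 4.4. The Expanded Extension for continuing subjects is 192 − 48 = 144 weeks, as the Table 4 title says. Quantity per dispensing is not stated, so it is an assumption and is varied.

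| | Dispensing marked | Blank, treatment continues | Blank, end of dosing |
|---|---|---|---|
| Table 4 | Wk 60, 72, 84, 108, 120, 132, 156, 168, 180 | Wk 96, 144 | Wk 192 |
| Table 5 | Baseline 2, Wk 12, 24, 36, 60, 72, 84, 108, 120, 132 | Wk 48, 96 | Wk 144 |

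**Supply of 12 weeks (one visit interval).** Weeks covered = dispensings × 12.
- Table 5: 10 × 12 = 120 of 144. Uncovered: Wk 48–60 and Wk 96–108.
- Table 4 from Wk 60: 9 × 12 = 108 of 132. Uncovered: Wk 96–108 and Wk 144–156. If drug is also dispensed at Extension Week 48, it is 10 × 12 = 120 of 144. The Table 3 dispensing row is not legible in the text available, so that point is assumed. Without it, Wk 48–60 would be a third uncovered stretch.
- Both tables, with that assumption: 144 − 120 = 24 weeks, and 24/144 = 16.7%.

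**Other quantities.**
- 13 weeks, surplus not carried over: each gap is 12 − 1 = 11 weeks, two per table.
- 13 weeks, surplus carried over (Table 5): 4 × 13 = 52, so the first gap is Wk 52–60, 8 weeks. Then 60 + 3 × 13 = 99, so the second is Wk 99–108, 9 weeks.
- 24 weeks: no gap in Table 5, and none in Table 4 from Wk 60.
- With full carry-over, 16 weeks would already suffice. Three dispensings must span 48 weeks, and 48/3 = 16.

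**Assessments affected, 12-week case.** SARA and liver tests at Table 4 Wk 108 and Wk 156, and Table 5 Wk 60 and Wk 108, would fall 12 weeks after supply ran out. That is 2 of 12 scheduled 12-weekly visits per table.

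**Effect of the on-treatment rule.** Twelve weeks is 84 days. A visit 84 days after a final dose lies outside both the addendum's 7-day on-treatment limit and its window of 8 to 21 days for the final study visit. The same visit 84 days after the last supplied dose, with dosing resumed afterwards, precedes the final dose and is classed as on-treatment.

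**The case against.** The strongest reply is that this is a clerical omission with little practical effect. The text tells sites how long treatment runs, and withholding drug from a continuing subject would contradict it. Two of the four columns double as early-discontinuation visits, where a blank is correct for someone stopping. No passage states the quantity per dispensing. Section 7.2.1 refers to bulk bottles, and the ±7-day visit window suggests some supply beyond 12 weeks. The schematic footnote also says dosing need not be continuous for subjects who had already completed the 48-week Extension.

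Part of this stands. The size of any gap depends on the unstated quantity, and the documents do not show that any subject went without drug. The rest does not remove the conflict. The other two blank columns have no early-discontinuation label. The schematic footnote most naturally covers the break before re-entry. The courier footnotes apply only when COVID-19 prevents a visit. Section 7.2.1 has Expanded Extension bottles assigned manually, so it describes no system allocation that would override the table.

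A reader might infer more than the documents support:
- That every subject loses 24 weeks. Only those treated past both visits could, and only with short supplies.
- That off-drug SARA scores would drive offers of 280 mg. The synopsis and Section 7.2 tie the qualifying decline to the first Extension Phase, before all the affected visits, although Section 4.1 omits that limit.
- That liver tests would look better after a gap. No figure in the documents shows this.
- That repeated visit numbers will merge Wk 60 and Wk 108 data. That depends on the database key, which is not shown, and the week labels differ.

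**Conclusion.** The inconsistency is real and of moderate importance. Four mid-phase visits have no dispensing marked, and no footnote or text supplies it. The same pattern in all six blocks suggests former end-of-phase columns that were not updated as the phase was extended, and makes a PDF-reading error unlikely.

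The size is conditional: up to 24 of 144 weeks (17%) per subject treated past both visits if each dispensing lasts 12 weeks, less with somewhat larger supplies, and nothing at 24 weeks. For Table 4 the 24-of-144 figure also assumes dispensing at Extension Week 48.

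The effect is confined to open-label exposure, compliance and long-term SARA and laboratory summaries. A reader might take it as a threat to the trial's main result, but the randomized 8-week comparison, its MMRM and the PGI-C test use none of these visits.

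**What to change.** 1. Reconcile the dispensing rows at Table 4 Wk 96 and Wk 144 and Table 5 Wk 48 and Wk 96 with the treatment duration in Sections 4.1, 4.3.3 and 4.4. Reconcile the Table 5 post-last-dose column after Wk 96 with the same sections. Which reading applies is for the sponsor to decide.
2. State the quantity supplied per dispensing, so that coverage between visits can be checked.
3. Give the Table 5 Wk 108 to Wk 144 visits, and the post-dose visit that follows, unique numbers.
4. For subjects already past these visits, use drug accountability records to identify real interruptions. Add a rule to the SAP addendum that flags SARA and laboratory results collected during them in the long-term summaries.

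The cost is small: table edits in an amendment or administrative letter, one added analysis rule, and a check of accountability data the protocol already collects.
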